1. AMENDMENT HISTORY

Amendment No.	Protocol Version No.	Date issued	Author(s) of changes	Details of Changes made
0	1	15/11/2023		Initial draft
1	2	24/04/2024	[name]	REC recommendations
2	3	08/06/2024	[name]	REC recommendations
3	4	04/07/2024	[name]	Change to neonatal age (<3months to < 2 months)

2. SYNOPSIS

Study Title	Application of Point of Care Testing (POCT) Full Blood Count (FBC) analyser in neonatal (<2 months) clinical care
Study Design	Laboratory and POCT analysis
Participants	Neonatal patients < 2 months of age
Planned Sample Size	30
Study Period	01/06/2024 – 31/09/2024
Primary Objective	To ascertain whether the device is suitable for a larger scale CE marking research project to enable clinical use of the device in neonates< 2 months of age.
Secondary Objective	To determine whether the device could offer a solution for the clinical issue of clotted samples from this population group.

3. ABBREVIATIONS

AE	Adverse event
AR	Adverse reaction
GP	General Practitioner
HDFT	Harrogate and District NHS Foundation Trust
ICF	Informed Consent Form
IPS	Integrated Pathology Solutions
NHS	National Health Service
PICU	Paediatrics Intensive Care Unit
PI	Principal Investigator
PIL	Participant/ Patient Information Leaflet
POCT	Point of Care Testing
R&D	NHS Trust R&D Department
REC	Research Ethics Committee

4. BACKGROUND AND RATIONALE

Performing a full blood count (FBC) is a common clinical practice in neonatal care. Samples reported as “clotted” are not able to be analysed and require redraw. A perceived “high” clotting rate elicits frustration among clinical team members and has negative effects on patient flow and patient satisfaction. The overall % rejection rate of neonatal FBC samples due to the presence of clots is high and has been estimated at 20-30% by the neighbouring neonatal units in large teaching hospitals in the region. The literature confirms clotting rejection rate of 30%.¹ Capillary blood is the main technique used to collect blood from neonates. Typically, platelet activation is triggered when there is a break in the vascular endothelium (heel prick). There are studies indicate that capillary blood sampling collection increases the risk of clotting.² There were preliminary evidence show that venous samples have a lower clotting rate but the latter is not an option except in few PICU cases. There are few postulated mechanisms for the cause of clotting in neonates such as the sample transfer time to the laboratory, the blood collection technique, prematurity, neonate weight or coexisting maternal or neonate’s clinical conditions. A recent study demonstrated that a child's increasing body weight reduced the risk of pre-analytical errors, including risk of clotting.² Therefore, the clotting rate is not a large pre-analytical problem in neonates older than 3 months old. However, to date, there are no studies to elucidate the main reason for the high clotting rate in neonates.

There has been ongoing audit work undertaken to establish the exact cause of why these samples seem to be clotting. Sampling technique and a change in blood collection bottles have been considered and implemented but with no clear consistent root cause being identified.³

Recently, POCT devices that measure FBC at the patient bedside have become available for clinical use and as such provide the potential to reduce the risk of clot formation. Currently, there are only two commercial POCT devices available for FBC measurement, both of which are not clinically validated for the age group from 0-3 months old. The HemoScreen is one of the two devices, which has a small footprint, requires a small sample of capillary or venous blood (40µL in each capillary) and gives 20 FBC results in 5 minutes across the 5-part differential. This device however, has only been clinically validated for patients 2 month old and onward. To realise the full potential of HemoScreen POCT device, it needs to be clinically validated in neonates < 2months old.

Although, HemoScreen POCT device is CE marked and clinically validated in the age group of > 2 months old onward. It is important to mention that HemoScreen is reasonably new to the healthcare market; hence, clotting studies for the <2 months old are not available yet.

5. OBJECTIVES

5.1 Primary Objectives

To ascertain whether the device is suitable for a larger scale CE marking research project to enable clinical use of the device in neonates< 2months of age.

5.2 Secondary Objectives

To determine whether the device could offer a solution for the clinical issue of clotted samples from this population group.

6. ELIGIBILITY

Participants will be neonatal patients resident at Special Care Babies Unit (SCBU) at Harrogate Hospital. The GCP trained neonatal unit nurses will do recruitment verbally. Potential participant's guardian will be approached and their child will be invited to participate, they will be provided with an information sheet about the study (**Attachment 1**) and they will be allowed at least 24h to think about participation. Enrolment is voluntary will only be accepted the guardian of the child signs an informed consent form (**Attachment 2**)

Inclusion Criteria:

1. Patients 2 months old or younger.

Exclusion Criteria:

1. Patient over 2 months old.
2. Participants in another research study involving an investigational product in the past 12 weeks.

7. ENROLMENT

7.1 Description of Enrolment Process

[figure not shown]
Subjects will be recruited by the staff nurses involved in the trial approaching the parents on the ward. Participant's guardians will be issued with an information sheet outlining the trial requirements and aims. The study will be discussed and participants parents will be made aware they do not have to take part in this trial.

7.2 Informed consent

The participant's guardian will personally sign and date the approved version of the informed consent form before any study specific procedures are performed. Written and verbal information will be presented to the participants guardian detailing the exact nature of the study and any risks involved in taking part. (Appendix) It will be clearly stated that the participant is free to withdraw from the study at any time for any reason with no obligation to give the reason for withdrawal. The participant guardian will be allowed as much time as wished to consider the information, and the opportunity to question the Investigator, their GP or other independent parties to decide whether they will participate in the study. Written Informed Consent will then be obtained by means of participant guardian dated signature and dated signature of the person who presented and obtained the informed consent. A copy of the signed Informed Consent will be given to the participants guardian. The original signed form will be retained at the study site.

7.3 Sample Collection

The sample collection, analysis and storage is outlined below:

1. When the patient's clinical care requires a FBC result, the sample will be collected with from the baby's heel (capillary) or as a venous sample into a purple topped paediatric EDTA tube. The standard quantity that is collected for this analysis is 400µL.
2. The sample will then be mixed to ensure dispersion of the EDTA anticoagulant through the blood and to ensure an even distribution of blood products. From this sample, 40µL will be drawn from the blood that has collected from the lid of the sample into the HemoScreen capillary sample collection device. The sample collection device will be placed into the HemoScreen cartridge and processed on the analyser by a trained user.
3. The FBC and 5 part differential results will be stored on the analyser and collected by the principal investigator. The clinical team will not report or act on these results.
4. The remaining sample will be labelled up and sent to the laboratory with a request card for FBC analysis.
5. The Laboratory sample will be processed as usual on the Sysmex XN1000 for FBC including 5 part differential.
6. The results will be reported to the clinical team for clinical management. The EDTA sample will be stored in the laboratory for a few days and then disposed as per normal laboratory procedure.

7. The laboratory results will be statistically compared to the retrieved results from HemoScreen (using Altman Bland and Passing Bablock Regression).

7.4 Target recruitment

A minimum of 15 patients are to be recruited to make a library of a minimum of 30 samples (max. 2 samples per single patient) is recommended by Altman and Bland graphical method as described in the Lancet 1986³⁷. This sample size would give a 95% Confidence Interval (CI) of about +/- 0.34S, where S is the standard deviation of the difference of the two methods used in this study (HemoScreen and Sysmex).

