8.6 Termination Criteria

A clotting rate of 10% on the Hemoscreen will result in the early termination of the study. The study will run until we have collected 30 suitable samples. Once we have the data from 30 samples the trial will close

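### Section 7.4 plans precision on 30 samples from as few as 15 infants with no allowance for correlation within an infant; if that correlation is positive, standard confidence intervals are too narrow by a factor of up to 1.41

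*Protocol*

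**What the plan says.** Section 7.4 sets the size of the study in two units. For infants: "A minimum of 15 patients are to be recruited". For blood samples, the target is "a library of a minimum of 30 samples (max. 2 samples per single patient"). At the minimum of 15 infants, every infant must supply two samples. The same section gives one precision figure: "This sample size would give a 95% Confidence Interval (CI) of about +/- 0.34S". Here S denotes a single SD of the between-method differences, not split into between-infant and within-infant parts.

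Section 7.3 (step 7) gives the analysis: "The laboratory results will be statistically compared to the retrieved results from HemoScreen". The methods listed there are Bland-Altman and Passing-Bablok, and no form for repeated measurements is named. Section 8.6 closes the study on a count of samples: "The study will run until we have collected 30 suitable samples". In the synopsis, the row "Planned Sample Size" reads 30, with no unit.

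The protocol does not mention correlation within an infant, a design effect, or an analysis with one sample per infant.

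**The concern.** The usual Bland-Altman confidence intervals, and the usual intervals for a Passing-Bablok slope and intercept, treat each pair of readings as independent. Two differences between the same two analysers, taken on blood from the same infant, may share features of that infant that affect one method more than the other. The second sample then adds less than one sample's worth of information, and an interval computed as if there were 30 independent pairs is too short.

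At stake is how well this pilot pins down the bias and the limits of agreement. Those estimates would inform the decision in section 5.1 on a larger CE-marking project. The planning figure in 7.4 is also affected, because it is attached to the number of samples with no reference to the number of infants.

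**Working it through.** **Inputs.** From section 7.4: 30 samples, at least 15 infants, at most 2 samples per infant, 95% confidence, stated half-width 0.34S. Assumed, because the protocol gives no value: the within-infant correlation rho of the differences, over 0 to 1.

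**Step 1: the stated figure, with independent pairs.**

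- Bias: half-width = 1.96·S/√n. At n = 30, 1.96/√30 = 0.358S (0.373S with the t quantile).
- Limit of agreement: Var ≈ S²/n + 1.96²·S²/(2n) = 2.92·S²/n, commonly rounded to 3S²/n. At n = 30, 1.96·√(3/30) = 0.620S (0.647S with t; 0.612S with 2.92 in place of 3).
- Sample size that 0.34S implies: for the bias, (1.96/0.34)² = 33.2; for a limit of agreement, 3·(1.96/0.34)² = 99.7.

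So ±0.34S is not reproduced at n = 30 for either quantity. It matches a limit of agreement with about 100 pairs. It also lies below the independent-pairs figure for the bias, so it cannot contain a hidden allowance for positive correlation.

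**Step 2: two samples from each of 15 infants.**

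- Bias: Var = S²(1+rho)/30; effective n = 30/(1+rho).
- Limit of agreement: Var ≈ S²[(1+rho) + 1.92(1+rho²)]/30.
- Example at rho = 0.5: bias 1.96·√(1.5/30) = 0.438S; limit 1.96·√((1.5 + 1.92·1.25)/30) = 1.96·√(3.9/30) = 0.707S.

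Coverage of the unadjusted 95% t intervals was simulated with normal differences, 15 infants × 2 samples, 100,000 runs per value of rho.

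| rho | Effective n (bias) | Half-width, bias | Half-width, limit | Width ratio, bias / limit | Coverage, bias | Coverage, limit |
|---|---|---|---|---|---|---|
| 0 | 30 | 0.358S | 0.612S | 1.00 / 1.00 | 95.0% | 94.5% |
| 0.2 | 25 | 0.392S | 0.640S | 1.10 / 1.05 | 92.6% | 93.4% |
| 0.5 | 20 | 0.438S | 0.707S | 1.22 / 1.16 | 89.0% | 90.4% |
| 0.8 | 16.7 | 0.480S | 0.796S | 1.34 / 1.30 | 85.0% | 85.8% |
| 1 | 15 | 0.506S | 0.865S | 1.41 / 1.41 | 82.1% | 82.0% |

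**Step 3: what limits the effect.**

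- The bias estimate stays unbiased. The expected value of S² changes only by the factor 1 − rho/29, which is 0.983 at rho = 0.5 and 0.966 at rho = 1, so the estimated limits barely move.
- If k infants supply the 30 samples, 30 − k of them give two. The variance inflation for the bias is then 1 + rho·2(30−k)/30. At rho = 0.5 it is 1.50 with k = 15, 1.33 with k = 20, and 1.00 with k = 30.

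**Step 4: does the remedy work with 15 infants?** Intervals from between- and within-infant variance components, with t quantiles on 14 degrees of freedom, covered about 95% for the bias and 94% to 96% for a limit of agreement across rho 0 to 1. A percentile bootstrap that resampled the 15 infants covered a limit of agreement only about 88%, 87%, 85% and 83% at rho 0, 0.2, 0.5 and 0.8. That is no better than the unadjusted interval at any of these values.

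**The case against.** The strongest reply is that the protocol names its methods only in general terms. It never says that pairs are treated as independent, and an analysis plan not shown here could specify the repeated-measurements form. This stands in part: the reported intervals could still be put right there. The planning statement could not, because section 7.4 itself ties one precision figure to a count of samples.

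It can also be said that the size of the effect is unknown, and this stands. The documents give no value for rho. Errors specific to a single sample, such as the handling before each reading, would push it down. At rho = 0.2 a limit of agreement is only 5% wider, and at rho = 0 nothing changes. All the tabled figures assume the minimum of 15 infants.

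Two stronger readings are tempting, and the documents do not support them:

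- A reader might infer that the go/no-go decision is distorted. The success rule in section 8.5 is a proportion of results within 2 SD and uses no confidence interval, so a short interval does not by itself change whether the criterion is met.
- A reader might infer that the synopsis promises 30 infants and so contradicts 7.4. The synopsis gives 30 in a row of its own with no unit, and 30 samples agrees with 7.4 and 8.6. The unit is unlabelled; the figures do not conflict.

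**Conclusion.** The point holds in a conditional form. Section 7.4 plans by the sample and makes no allowance for two samples from one infant. If the differences are positively correlated within infants, standard intervals are too narrow by a factor of √(1+rho) for the bias and somewhat less for the limits, at most 1.41 for either. It would go too far to say that the intervals will be too narrow: that needs a positive rho, which is plausible but not documented, and an analysis that ignores the pairing, which the protocol neither states nor rules out.

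The sizes rest on normal differences, equal correlation in all infants, and exactly 15 infants with two samples each. In a pilot of 30 samples this is a moderate weakness that is cheap to correct. The ±0.34S figure is wrong for 30 pairs whatever rho is. For a limit of agreement, the gap from 0.34S to 0.62S is larger than what clustering adds at any rho (0.61S to 0.87S at the extreme).

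**What to change.** - State in 7.4 that the infant is the independent unit and that samples are nested within infants.
- Use the Bland-Altman method for repeated measurements, with between- and within-infant variance components and t-based intervals on infant-level degrees of freedom. Do not rely on a percentile bootstrap of 15 infants for the limits of agreement.
- Add a sensitivity analysis with the first sample per infant only, for both Bland-Altman and Passing-Bablok.
- Replace ±0.34S. Say whether the figure refers to the bias or to a limit of agreement, and give it as a range over rho. At 15 × 2 and rho from 0 to 1, that is about 0.36S to 0.51S for the bias and 0.61S to 0.87S for a limit.
- Label the synopsis figure of 30 as samples and give the minimum number of infants beside it.

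The cost is slightly wider intervals, some rewording, and a little analysis work that may fall outside the Excel add-in named in section 8.3. No further blood samples or recruitment are needed.

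### The precision of about ±0.34S stated for 30 samples names no quantity and does not reproduce, either for a limit of agreement (about ±0.62S to 0.65S) or for the mean difference (about ±0.36S to 0.37S)

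*Protocol*

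**What the plan says.** Section 7.4 sets the size: "A minimum of 15 patients are to be recruited to make a library of a minimum of 30 samples (max. 2 samples per single patient"). It attributes this number to the Bland-Altman graphical method, citing a 1986 paper, and then gives its only numerical statement of precision: "This sample size would give a 95% Confidence Interval (CI) of about +/- 0.34S". The unit S is defined there as the SD of the paired HemoScreen-minus-Sysmex differences. The quantity to which the interval belongs is not named.

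The Synopsis also gives a planned size of 30. Section 8.6 makes 30 the stopping point as well as the minimum: "Once we have the data from 30 samples the trial will close". Section 7.3 plans the comparison "using Altman Bland and Passing Bablock Regression".

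**The concern.** S is only a unit of scale, so the half-width in multiples of S depends on the number of pairs and on the quantity being estimated. It can therefore be checked without any data. A Bland-Altman analysis normally reports two quantities with intervals: the mean difference (bias) and each limit of agreement, which is the mean difference ± 1.96S. The stated figure should match one of these at n = 30, and it matches neither.

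What is at stake is how a reader judges the pilot. The primary objective is to decide whether the device merits a larger CE-marking study. Someone who takes ±0.34S as the precision of the limits of agreement would think them known about twice as well as 30 pairs allow, and could carry that belief into planning the multi-centre study mentioned in section 14.

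**Working it through.** **Inputs**
- n = 30 pairs (sections 7.4 and 8.6, Synopsis).
- Two-sided 95% interval: z = 1.96, or t on 29 degrees of freedom = 2.045.
- S: SD of the paired differences, used only as the unit (section 7.4).
- Stated half-width: 0.34S (section 7.4).
- Independence of the 30 differences is assumed in steps 1 to 4.

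**1. Attempt to reproduce 0.34S as the interval for the mean difference**

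Half-width = z·S/√n.
- With z: 1.96/√30 = 0.358S. Ratio to stated: 0.358/0.34 = 1.05.
- With t: 2.045/√30 = 0.373S. Ratio: 0.373/0.34 = 1.10.
- Solving for n: (1.96/0.34)² = 33.2.

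This is close, but 0.34S is not the value at 30.

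**2. Attempt to reproduce it as the interval for a limit of agreement**

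Variance = S²/n + 1.96²S²/(2(n−1)), roughly 3S²/n, so half-width ≈ z·S·√(3/n).
- With z: 1.96·√(3/30) = 0.620S. Ratio: 0.620/0.34 = 1.82.
- With the full variance: 1.96·√(1/30 + 3.8416/58) = 0.618S.
- With t: 2.045·√(3/30) = 0.647S. Ratio: 0.647/0.34 = 1.90.

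**3. Where 0.34S does arise**

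For a limit of agreement, n = 3·(1.96/0.34)² = 99.7. At n = 100, 1.96·√(3/100) = 0.339S. The stated figure is the limit-of-agreement value for 100 pairs.

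**4. Other candidates**
- 90% interval for the mean difference, n = 30: 0.30S (z) or 0.31S (t).
- 95% interval for the SD, normal approximation, n = 30: 1.96/√58 = 0.26S.
- 95% chi-square interval for the SD, n = 30: −0.20S to +0.34S. The upper arm agrees with the stated number, but the interval is not symmetric, so it is not a ± figure and the match looks like coincidence.
- n = 15, one difference per infant (z): 0.51S for the mean difference, 0.88S for a limit of agreement.

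No candidate gives a symmetric 95% interval of ±0.34S at n = 30.

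**5. Illustration of two samples per infant**

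The protocol gives no within-infant correlation ρ of the differences, so a range is assumed. For 15 infants with two samples each, the approximate variance of a limit of agreement is S²[(1+ρ) + (1.96²/2)(1+ρ²)]/30, and that of the mean difference is S²(1+ρ)/30. Half-widths with z:

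| Assumed ρ | Limit of agreement | Mean difference |
|---|---|---|
| 0 | 0.61S | 0.36S |
| 0.25 | 0.65S | 0.40S |
| 0.50 | 0.71S | 0.44S |
| 0.75 | 0.78S | 0.47S |

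The first row is 0.61S and not 0.62S because this approximation uses 1 + 1.96²/2 = 2.92 where step 2 rounds to 3.

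**The case against.** The strongest reply is that section 7.4 never says the interval is for a limit of agreement. If the mean difference was meant, the text says *about* 0.34S and the z-based value is 0.358S, a gap of 5% with little practical consequence. This stands in part. The factor of 1.8 depends on the limit-of-agreement reading, which is inferred from the method cited and from the close match at 100 pairs; the document does not state it. Nor does the citation settle the matter: it carries the number 37, while the reference list ends at 3. Even so, the mean-difference reading still fails to give the stated value at 30. The word *minimum* in section 7.4 does not help, because 33 pairs would be needed and section 8.6 closes the study at 30.

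A second reply is that nothing in the study turns on the figure. That is correct for the stated rules. The success criterion in section 8.5 counts HemoScreen results within 2 SD of the laboratory, and the early-termination rule in section 8.6 uses a clotting rate. Neither uses an interval around a limit of agreement. Section 14 calls the study a pilot and expects a larger multi-centre study before clinical use.

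Third, section 7.4 also rests the 30 samples on a recommendation attributed to the cited paper. That source is not available here, so this ground can be neither confirmed nor dismissed, and the precision figure should not be called the whole case for the sample size.

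**Conclusion.** The precision statement in section 7.4 is wrong as written under either standard reading, and it does not say which reading applies. For a limit of agreement the half-width at 30 independent pairs is about 0.62S (z) or 0.65S (t), which is 1.8 to 1.9 times the stated 0.34S. For the mean difference it is 0.36S (z) or 0.37S (t), 5% to 10% above the stated value. The figures assume independent, roughly normal differences. Any widening from repeat samples depends on positive within-infant correlation, for which the protocol gives no value.

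A reader might infer three stronger conclusions that the documents do not support:
- *That the protocol certainly overstates its precision nearly twofold.* This holds only if limits of agreement were meant, which is likely but not stated.
- *That the study is too small and needs 100 samples.* The protocol sets no target precision that a pilot must reach; 100 is only the number at which 0.34S would be true for a limit of agreement.
- *That the success criterion or the decision on a larger study is invalidated.* No stated rule uses the figure.

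This is a correction to the protocol's only numerical precision claim, not to its design or its success criterion.

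**What to change.** In section 7.4, name the quantity and give the half-width on one convention, using z or t for both figures. For example, with t:

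> *If the paired differences were independent, 30 samples would give a 95% CI of about ±0.65S around each limit of agreement and ±0.37S around the mean difference; with two samples per infant, positive within-infant correlation would widen these.*

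If the sponsor intended only one of the two quantities, it should keep that one and say so. The z-based pair is ±0.62S and ±0.36S. The citation number should be matched to an entry in the reference list at the same time.

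The cost is one sentence. It needs no extra infants, blood samples or study time and changes no decision rule; the stated precision becomes less favourable.
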